9.5 Blinding and code-breaking

Standard surgical practise will be followed. Patients are not formally blinded to which Surgeon (Consultant, Fellow, or StR) performs their operation, and are informed if requested. In line with standard surgical practise and training within the NHS, patients will provide informed consent that they understand no guarantees can be given that a particular person will perform the procedure. The person will, however, have appropriate experience.

Due to the nature of this study the StR's cannot be blinded to their allocations into either the 'control' or 'intervention' groups, however the assessment methods and any assessors will be blinded.

9.6 Description of study intervention(s),

The intervention to be tested is the simulation-based and cognitive learning package, which will be delivered to a randomised sub-group of 50% of the StR's recruited into this study. This will be delivered in a supervised setting within the OOSEC over a 4-week period for between 1 to 2 hours per week, over 3 to 4 consecutive but separate six-month placements (please see Appendix A for Study Flow Diagram). This will take place on a Wednesday afternoon, which is when all the Regional StR's are due to attend teaching in Oxford at the NOC.

The OOSEC is a secure enclosed laboratory space within the NOC, which contains all the necessary equipment required to run the simulation-based and cognitive learning training. The simulation training in general may include:

- 1) Focussed workshops on saw-bone models (simulated bones)
- 2) Digital and computer-based cognitive learning packages
- 3) Virtual reality platforms.

All participants within group 1 (StR's) will be asked to attend and complete baseline and final assessments within the OOSEC, which will consist of a multiple-choice questionnaire (MCQ) and a simulated procedure. Participants within group 2 (Consultants and Fellows) will only be required to complete a baseline simulated procedure.

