9.7 Intra-operative surgeon performance data collection

The following protocol will apply to all episodes of intra-operative performance data collection for StR's and Fellows. The intra-operative data collection for Consultant performed operations will differ slightly in that they require no supervision, and no surgeon will 'take over' the operation. However, the methods for recording the intra-operative data will remain the same.

A maximum of two study participants (excluding Consultants) will attend any given list. The PI ([name]) will attend the World Health Organisation (WHO) briefing in theatre on the morning of the list, introduce themselves and explain their role during the list. If recording an StR, neither the participant or PI will disclose which arm of the study the participants are in (routine training, or additional simulation training). The supervising Consultant will confirm the cases on the list the StR or AF's will be performing under supervision and training.

Operative protocol

After anaesthesia and patient set-up, the supervising Consultant and participant will scrub in up in the usual manner with the motion sensors in position on the lead surgeon's elbows under their sterile gown (see Appendix C). The procedure will then continue routinely and normally, but with the PI collecting motion data via the wireless Bluetooth sensors. The PI will also manually record the timings of each stage of the THR operation. This process will allow synchronisation of motion data to the participants progression throughout the stages of the operation. Data collection will stop when the dressing has been applied to the surgical wound.

Following completion of the operation, the participants in conjunction with the supervising Consultant will be asked to complete short written assessments of the lead surgeons' intra-operative performance. These assessments may include: Global Rating Scales (GRS), Objective Structured Assessment of Technical Skills (OSATS), and surgical checklists.

Intra-operative deviations or interruptions

Sometimes the supervising Consultant needs to take over part or all of an operation if it proves particularly difficult. In the event that a procedure has to be taken over completely by the Consultant then data recording will stop. If minor adjustments only are made by the Consultant during the operation then these will be noted and time marked against the motion data.

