11 STATISTICS AND ANALYSIS

Analysis of motion data.

Motion data from the wireless sensors produces performance surrogate markers such as: the number of movements (major & minor); total path length; and smoothness/economy of movement. Data distributions will be assessed for normality using the Shapiro-Wilk test. Previous studies show such data are not normally distributed, and we would expect to use non-parametric tests, such as the Mann-Whitney U test to compare the performance metrics between the 2 groups of participants (StR's against Experts & Fellows). The Mann-Whitney U test will also be used to compare performance metrics between the two sub-groups of StR's (control and intervention), and also within the intervention sub-group in order to compare performance before and after training.

Performance metrics within all groups of participants will be reported using descriptive statistics to outline the central tendency (mean, median, and mode) and variation (range, variance, and standard deviation) in readings obtained. The Kruskal-Wallis one-way analysis of variance (ANOVA) test will be used to test for differences in the mean values obtained for all performance metrics between the two groups of participants. The Wilcoxon signed-rank test will be used to determine any differences in performance metric between the two groups.

Analysis of other routinely obtained data

X-ray (radiograph) analysis:

X-rays will be reviewed by two independent Consultant Orthopaedic Surgeons who will be blinded to the patient and lead surgeon's identity in order to reduce bias. There are several important parameters to be evaluated when reviewing a pelvic x-ray, therefore we will ask each reviewer to allocate a categorical global rating (see below) for both the pre- and post-operative x-rays. [5] The Chi-squared test will be used

to determine if there are any significant differences between each group, and also intra-group differences (for example StR's before and after additional training).

Pre-operative x-ray

- 1: Hip osteoarthritis without significant bone loss.
- 2a: Hip osteoarthritis with significant bone loss on acetabular side.
- 2b: Hip osteoarthritis with significant bone loss on femoral side.
- 3: Hip osteoarthritis with significant bone loss on both acetabular and femoral sides.

Post-operative x-ray

- 1: Excellent implant position and restoration of hip anatomy.
- 2a): Good overall with minor imperfections on acetabular side.

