- 2b): Good overall with minor imperfections on femoral side.
- 3: Moderate concerns but does not require revision surgery.
- 4: Significant concerns requiring revision surgery.

Every patients post-operative x-ray will also be reviewed by the PI ([name]) for acetabular component positioning (inclination and version) using the methodology described by Bachhal [4]. This continuous data will be assessed for normality of distribution, and analysed using similar methodology as described above for the motion data. We will be looking for any statistically significant differences between the 2 groups of participants, within the two sub-groups of StR's (control and intervention), and also within the intervention sub-group in order to compare performance before and after additional training.

Other outcomes data:

Following collection of the outcome measures listed below, the normality of the data distribution will be checked with the Shapiro-Wilk test. Descriptive statistics will be used to outline the central tendency and variation of these data sets. Statistical analyses between each group of participants will be performed using either the parametric unpaired t-test or a non-parametric Mann-Whitney U test depending on the distribution of the data. Subsequent analysis of the outcomes data using a paired t-test, or Mann-Whitney U test will also be performed within the two sub-groups of the StR's (control and intervention), and also within the intervention sub-group in order to compare outcomes before and after additional training.

- Theatre time usage.
- Blood loss (pre-/post-op haemoglobin levels)
- In-patient length of stay.
- PROMs: EQ-5D and OHS.

The Chi-squared test (or Fishers exact test if the sample is <5) will be used to determine any significant differences between the groups regarding the incidence of blood transfusions or peri-operative morbidity.

All of these tests will be performed using the SPSS statistical package, which is available for any registered student on the University of Oxford current Licencing agreement.

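### Cup inclination and version are read by the PI alone with no masking described, although the PI attends the operations and section 9.5 says assessors will be blinded

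*Combined protocol and SAP*

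**What the plan says.** Section 11 plans two separate readings of the post-operative film.

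- **Global grade.** A categorical rating of the pre- and post-operative films is given by "two independent Consultant Orthopaedic Surgeons who will be blinded to the patient and lead surgeon's identity in order to reduce bias".
- **Cup position.** "Every patients post-operative x-ray will also be reviewed by the PI" for inclination and version, using a cited published method. No masking, coded images, reading order, second angle reader or agreement check is described. The angles are then handled as continuous data: "This continuous data will be assessed for normality of distribution". The listed comparisons are between the two participant groups, across the two registrar sub-groups (which I read as control versus intervention), and before versus after training.

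Two other sections bear on this. Section 9.5 says that "the assessment methods and any assessors will be blinded" and stops there. Section 9.7 places the PI at the theatre briefing, has the PI collect the motion data and time the stages of the operation, and adds that "neither the participant or PI will disclose which arm of the study the participants are in".

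Section 6 lists X-ray analysis under the primary objective and cites the same reference that section 11 uses for the cup measurement.

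**The concern.** The plan recognises observer bias for one reading of the film and protects against it. It then leaves the other reading, of the same film, to the member of the team who is probably least able to be blind. Inclination and version are the only continuous radiographic measures in the plan. If the reader's knowledge of who operated, or of who was trained, affects the readings even slightly, the effect enters the comparison as though it were a difference in surgical performance.

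Two comparisons are exposed. Registrars versus Experts and Fellows is exposed simply because the PI saw who operated. The randomised comparison is exposed if, as section 9.7 implies, the PI also knows the arm. With a single angle reading per film, the planned data could not separate a reading effect from a real one.

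**Working it through.** **1. The plan's own numbers.** The synopsis gives 193 patients: 16 × 8 + 8 × 5 + 5 × 5 = 128 + 40 + 25 = 193, which reproduces. At 1:1 allocation (section 7), 128 / 2 = 64 hips per registrar arm. Sections 8.1 and 9.4 also allow 6 registrars per arm, which gives 6 × 8 = 48. The plan contains no SD, effect size, power or reading error for cup position, so there is no further figure to reproduce.

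**2. The passages side by side.**

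| Question | Global grade | Cup inclination and version |
|---|---|---|
| Reader | Two independent Consultants | The PI |
| Masking described in section 11 | To patient and lead surgeon | None |
| Present at the recorded operations | Not stated | Yes (section 9.7) |
| Knows the arm | Not stated | Implied by section 9.7 |

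Attendance settles the first point: the PI knows who the lead surgeon was. Knowledge of the arm is an inference. An instruction not to reveal the arm has little purpose unless the person holds it. Section 9.2 also has the PI or a deputy take consent, with registrars randomised after enrolment. Section 9.4 does not say who opens the envelope. Section 9.5 promises blinding in general, but nothing shows how it would work for a reader who was in theatre.

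**3. Illustration of size.** All inputs here except the number of hips are assumptions.

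- Between-hip SD: 5 to 8 degrees.
- Differential shift in mean reading between arms: 1 to 2 degrees, with no true difference.
- Two-sided 5% z-test.
- Design effect: 1 + (8 − 1) × ICC, which is 1 at ICC 0 and 2.4 at ICC 0.2.
- SE = SD × √(2 × design effect / n per arm).
- False-positive rate = Φ(shift/SE − 1.96) + Φ(−shift/SE − 1.96).

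| Hips per arm | ICC | SD, shift (degrees) | SE | Shift/SE | False-positive rate |
|---|---|---|---|---|---|
| 64 | 0 | 8, 1 | 1.41 | 0.71 | 11% |
| 64 | 0 | 5, 2 | 0.88 | 2.26 | 62% |
| 64 | 0.2 | 8, 1 | 2.19 | 0.46 | 7% |
| 64 | 0.2 | 5, 2 | 1.37 | 1.46 | 31% |
| 48 | 0.2 | 8, 1 | 2.53 | 0.40 | 7% |
| 48 | 0.2 | 5, 2 | 1.58 | 1.26 | 24% |

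The ICC 0.2 rows suppose that the analysis allows for clustering by surgeon. The 62% is the extreme corner: smallest SD, largest shift, largest sample and no clustering.

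**The case against.** **Section 9.5 already covers the PI.** Read literally, a promise that any assessors will be blinded includes the person measuring the films. But no mechanism is given, and the promise sits badly with section 9.7. It turns the problem from a plain omission into an inconsistency, and does not remove it.

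**Arm knowledge is not stated.** This stands. A reader might infer that the plan says the PI knows the allocation; it only implies it. Nor do the documents say how films reach the PI. Section 12.4 uses study identifiers on study documents, though it is not stated that these would hide the surgeon from the PI. Knowledge of the lead surgeon rests on attendance and does not depend on the arm inference.

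**There is a check on the angles.** In part. The masked Consultants grade the same films and have a category for minor acetabular imperfections. A reader might infer that nothing independent exists; that goes too far. The grade is a coarse check on placement and cannot show a shift of a degree or two. What is missing is a second reading of the angles.

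**The size is guesswork.** This also stands. The plan names no target angle and no better direction, so a reader who favoured one arm has no evident way to push the mean. A pull towards an ideal angle might narrow the spread and leave the mean where it was. A set measurement method may also leave less room for bias than a subjective grade; the documents do not describe the method closely enough to tell.

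**The PI's thesis.** Section 20 says that the results form part of it. That is not evidence of biased measurement, and the point does not rely on it.

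**Conclusion.** The point holds as a gap and an internal inconsistency. Sections 9.5, 9.7 and 11 cannot all be followed for the cup-angle reading as planned unless some masking is added that the plan does not describe. Two continuous outcomes under the primary objective are left open to observer bias, in the randomised comparison and in registrars versus Experts and Fellows.

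The documents show a risk. They do not show that bias would occur, how large it would be or in which direction. The figures of 11% to 62% without clustering, and 7% to 31% at ICC 0.2, depend wholly on the assumed SD, shift and ICC, and on the bias moving the mean. They show that a shift small beside the spread between hips could matter with 64 hips per arm, and should not be quoted as an estimate for this trial. The change should be made because it is cheap and extends a safeguard that the plan already uses.

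**What to change.** In section 11, put the angle reading under the same masking as the global grade:

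1. A research-team colleague exports the post-operative films without name, date, hospital or study identifier, under a random code and in random order.
2. The PI reads inclination and version in one batch after the last operation.
3. The angles are locked before the code is linked to surgeon and arm.
4. Section 9.5 is reworded to say how this reading is masked, and is reconciled with section 9.7.

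**Cost.** Some hours of image handling and a short change of text, with whatever approval section 16.6 requires if the change counts as substantial. No extra X-ray or extra reader is needed. The angles become available only at the end of the study. Masking stays imperfect if the PI remembers a particular film. If that residual weakness matters to the sponsor, a reader who did not attend the operations, or a second reading of a sample with an agreement statistic, would reduce it at the price of another person's time.

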6. OBJECTIVES AND OUTCOME MEASURES

Objectives	Outcome Measures	Timepoints of evaluation
Primary To assess the impact of simulation training on surgical trainee performance and patient outcomes following THR.	Participants: 
 Wireless motion data metrics from elbow worn sensors (hand movements, path length and time taken) Global Rating Scales (GRS). Objective Structured Assessment of Technical Skills (OSATS). Surgical checklists. Patients: 
 X-ray analysis of THR.[4] Blood loss and transfusion rates. Peri-operative patient morbidity In-patient length of stay. PROMs: EQ-5D and OHS. 	Intra-operative assessments to be performed at a minimum of 8 separate THR operations for each participant in Group 1 (StR'S) over a 6-month period. Outcome measures data will be collected for all patients who have had a THR performed by any participant as the lead surgeon in this study.
Secondary To define an expert standard when performing a primary elective THR. To determine if operative surgeon performance metrics during a THR relate to surgical experience, or patient outcomes.	Participants: 
 Wireless motion data metrics from elbow worn sensors (hand movements, path length and time taken) Patients: 
 X-ray analysis of THR.[4] Blood loss and transfusion rates. Peri-operative patient morbidity In-patient length of stay. PROMs: EQ-5D and OHS. 	Intra-operative assessments at a minimum of 5 separate THR operations for each participant in Group 2 (Experts & Fellows). Outcome measures data will be collected for all patients who have had a THR performed by any participant as the lead surgeon.

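### Cup inclination and version go to tests of location with no reference angle, so a gain in placement accuracy could be missed or not recognised as a gain, and a neutral shift could be called a difference

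*Combined protocol and SAP*

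**What the plan says.** The objectives table in Section 6 lists "X-ray analysis of THR.[4"] under the primary objective. Its reference 4 is the method that Section 11 uses for the cup angles.

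Under X-ray analysis, Section 11 has the principal investigator read "acetabular component positioning (inclination and version") on each patient's post-operative film. It then states: "This continuous data will be assessed for normality of distribution, and analysed using similar methodology as described above for the motion data". The aim is given as "We will be looking for any statistically significant differences between the 2 groups of participants", and the same is to be done within the two registrar sub-groups.

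The methods carried over are in the motion-data part of Section 11:

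- A Shapiro-Wilk check of normality.
- Mann-Whitney between registrar arms: "The Mann-Whitney U test will also be used to compare performance metrics between the two sub-groups of StR's (control and intervention").
- Kruskal-Wallis, which "will be used to test for differences in the mean values obtained for all performance metrics".
- Wilcoxon signed-rank.
- Spread, reported descriptively: "variation (range, variance, and standard deviation) in readings obtained".

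No target angle, tolerance, absolute deviation or test of spread for the angles appears in the document.

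Separately, two blinded Consultants give each film a categorical global rating, whose top grade reads "1: Excellent implant position and restoration of hip anatomy". It is compared by chi-squared.

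**The concern.** Path length, number of movements and time have a natural direction, so a test of location on them can be read as better or worse. Inclination and version do not: a cup can be misplaced by being too high or too low. A rank test on the angles asks whether one arm's cups sit systematically higher, not whether they sit closer to where they were meant to be.

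Three results can follow:

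- Training tightens placement around the same centre, and the test sees almost nothing.
- Training corrects a systematic offset, and the test flags a difference. With no reference stated, nobody can say from the test whether it is a gain or a loss.
- The arms sit on opposite sides of the intended position and are equally accurate, and the test reports a significant difference.

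Cup position is one of the few objective patient-side measures of technical quality in the trial, so a false null or an uninterpretable positive here matters.

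**Working it through.** **Inputs from the documents.** The Synopsis gives 8 patients for each of 16 registrars, 5 for each of 8 Fellows and 5 for each of 5 Consultants: 16×8 + 8×5 + 5×5 = 128 + 40 + 25 = 193, which reproduces the stated total. Section 7 gives 1:1 allocation, so each registrar arm has 8×8 = 64 hips. With the lower figure of 12 registrars in Section 8.1 it is 6×8 = 48. The plan contains no power calculation and no SD for either angle.

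**Assumptions, not in the documents.** Two-sided 0.05, normal errors, independent hips unless an ICC is stated, and the SDs and offsets shown.

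**Why spread is invisible to the test.** With equal centres the expected difference in location is 0, so a test of location rejects at about its alpha whatever the SDs. The mean absolute deviation does change. For a normal error centred on the reference it is SD×√(2/π): 10×0.798 = 7.98 degrees, 7×0.798 = 5.59, 5×0.798 = 3.99.

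**Why a neutral shift is visible.** Put one arm 2 degrees below the reference and the other 2 above, both at SD 7. By symmetry the mean absolute deviation is equal, 5.8 degrees in each arm. For the difference of 4 degrees between arms, the standard error is 7×√(2/64) = 1.237, the ratio is 4/1.237 = 3.23, and power is Φ(3.23 − 1.96) = Φ(1.27) = 0.90.

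**Simulated Mann-Whitney rejection rates, 64 v 64 hips.** Repeat runs differ by a point or two, hence the ranges.

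| Scenario | Angles as measured | Absolute deviation |
|---|---|---|
| Same centre, SD 10 v 8 | about 5% | 27–29% |
| Same centre, SD 10 v 7 | 4–5% | 58–60% |
| Same centre, SD 10 v 6 | 5–6% | 87–89% |
| Same centre, SD 10 v 5 | about 6% | about 99% |
| Neutral shift of 4 degrees, SD 7 | 87–88% | 5% |
| Neutral shift of 6 degrees, SD 7 | 99.6% | 4.5% |
| Offset of 5 degrees corrected to 0, SD 7 | 97% | 30% |

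With 48 hips per arm, absolute deviation gives 21%, 47% and 77% for the first three rows, and the test on the angles stays at about 5%.

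**Registrar as the unit (8 v 8 means of 8 operations).** For SD 10 v 7, a t-test on the angles rejects in about 5–6% of runs and on absolute deviation in 67–69%. For SD 10 v 6 it is about 5–6% v 92–94%. Setting the ICC at 0.10 hardly changes this (for 10 v 6, 5.4% v 92%).

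**Brown-Forsythe test of spread.** It needs no reference and gives 71% (10 v 7) and 96% (10 v 6). It has only about 5% power when an offset is corrected and the spread stays the same.

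**Cost of a badly placed reference.** If the reference lies 5 degrees from the registrars' common centre, registrar-level power on absolute deviation falls from 69% to 43% for SD 10 v 7, and from 93% to 67% for 10 v 6. At 8 degrees off, the first is 22%.

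**The case against.** The strongest reply is that the spread-only scenario is a choice. Nothing in the protocol says how simulation should change cup angles. If it corrects a systematic offset, the planned test is far the more sensitive (97% v 30%). This stands. A reader might infer that the planned analysis cannot show any benefit of training, or that the angles should only be described. The documents and the figures support neither reading. What remains is that a detected shift cannot be labelled gain or loss without a reference.

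Second, placement quality is not left wholly to the angles. The blinded global rating runs from better to worse and separates minor imperfections on the acetabular and femoral sides. Carrying over the motion-data methods also brings the SD and range, so scatter would be visible. Both are partial safeguards: the rating is coarse and does not use the measured angles, and the SD is described but not tested.

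Third, that the angles are tested as measured is inferred. The text says the methodology will be similar and does not expressly rule out a derived deviation. That is fair, but no other form is named, and an analyst following the text would test the angles themselves.

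Fourth, using the study's own Consultants as the reference has problems. Measuring deviation from their median favours Group 2 by construction in the registrar v Expert comparison. Section 8.1 also takes Consultants from one hospital only, while registrars come from two.

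**Conclusion.** The concern holds as stated in the heading. Under the assumed SDs, the planned test has about 5% power for a gain through tighter spread, even where mean absolute error halves (SD 10 v 5). It also calls a neutral 4-degree shift significant in close to nine runs in ten. The exact powers for absolute deviation depend on the assumed SDs and are modest for a small gain (27–29% for 10 v 8). The near-alpha rejection rate under a pure change in spread does not depend on the SDs, provided hips are independent or the registrar is the unit of analysis.

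It does not follow that accuracy goes unexamined or that the planned test is useless: it picks up a change of centre well. The angles are one part of one of nine items under the primary objective. This should be corrected before analysis, but it does not undermine the trial as a whole.

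**What to change.** In Section 11, under X-ray analysis:

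1. For the comparison of registrar arms, make the analysis of each angle the registrar's mean absolute deviation from a reference that the investigators choose and write down before any data are unblinded.
2. Add a Brown-Forsythe test of spread as a supporting analysis, since it needs no reference.
3. Report the signed mean difference with its confidence interval, and the SD per arm, alongside. Interpret direction only relative to the reference.
4. If the Consultant median serves as the reference, limit it to the comparison of registrar arms.

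The cost is a few sentences and no extra measurement. The downside is that a reference must be agreed in advance, and that power falls if it lies away from the registrars' centre. The supporting test of spread and the retained signed difference guard against that.
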